# 9.4.7 Calculation or derivation of pharmacokinetic variables

# 9.4.7.1 Population pharmacokinetics and exposure-response/safety analysis

A population PK model will be developed using a non-linear mixed-effects modelling approach. The impact of physiologically-relevant patient characteristics (covariates) and disease on PK will be evaluated. The relationship between the PK exposure and the effect on safety and efficacy endpoints will be evaluated. The results of such an analysis will be reported in a separate report. The PK, pharmacodynamics, demographic, safety, and efficacy data collected in this study may also be combined with similar data from other studies and explored using population PK and/or PK-pharmacodynamic methods.

# 9.4.7.2 Pharmacokinetic analysis

The actual sampling times will be used in the PK calculations. PK concentration data and summary statistics will be tabulated. Individual and mean blood concentration-time profiles will be generated. Samples below the lower limit of quantification will be treated as missing in the analyses.

# 9.4.7.3 Immunogenicity analysis

Immunogenicity results will be analyzed descriptively by summarizing the number and percentage of patients who develop detectable ADA to durvalumab and to tremelimumab. ADA titer and the presence of nAb will be reported for samples confirmed positive for the presence of

ADA. The effect of immunogenicity on PK, pharmacodynamics, efficacy, and safety will be evaluated, if the data allow.

#### 9.4.8 Calculation or derivation of biomarker variables

Biomarker status, as defined in the secondary and exploratory objectives, will be assessed for evaluable patients in each treatment group according to prespecified criteria that will be detailed in the SAP.

# 9.4.9 Calculation or derivation of pharmacogenetic variables (Not Applicable for China)

In the case of genetic data, only the date that the patient gave consent to participation in the genetic research and the date the blood sample was taken from the patient will be recorded in the eCRF and database. The genetic data generated from the study will be stored in the AstraZeneca Laboratory Information Management System (LIMS) database or other appropriate system. This database is a secure database, which is separate from the database used for the main study. Some or all of the dataset from the main study may be duplicated within the AstraZeneca LIMS database for exploratory genetic analysis. Data will be reported outside the CSR (please see Appendix D).

# 9.5 Statistical analyses

Analyses will be performed by AstraZeneca or its representatives. A comprehensive SAP will be developed and finalized before database lock and will describe the patient populations to be included in the analyses and procedures for accounting for missing, unused, and spurious data. This section is a summary of the planned statistical analyses of the primary and secondary endpoints. Any deviations from this plan will be reported in the clinical study report.

If this study achieves statistical significance for either of the dual primary endpoints of PFS and/or OS at one of the planned interim analyses, then that will be considered the primary analysis for that endpoint. Further analyses for that particular endpoint may still occur depending on the need to have long-term follow up or more mature data. The final analysis of the study will then be the last assessment of long-term benefit.

# 9.5.1 Efficacy analyses

The primary aim of the study is to assess the efficacy of durvalumab monotherapy versus placebo in terms of PFS (per RECIST 1.1 as assessed by BICR) and OS.

Descriptive statistics will be used for all variables, as appropriate, and will be presented by treatment group. Continuous variables will be summarized by the number of observations, mean, standard deviation, median, minimum, and maximum. Categorical variables will be summarized by frequency counts and percentages for each category. Unless otherwise stated, percentages will be calculated out of the population total for the corresponding treatment group.

In general, baseline will be the last observed assessment of the variable under consideration prior to the intake of the first dose of IP, except for efficacy variables. For efficacy variables (including PRO), baseline is defined as the last observed measurement prior to randomization.

All data collected will be listed. Efficacy and PRO data will be summarized and analyzed based on the FAS. PK data will be summarized and analyzed based on the PK Analysis Set. Safety data will be summarized on the SAS.

All outputs will be summarized by treatment group for all randomized patients (FAS). However, for analyses involving the durvalumab and tremelimumab combination treatment group, only those patients randomized up to and including the date of the 600th patient will be included in the analyses (combination analysis set, approximately 200 patients per arm).

Results of all statistical analyses will be presented using a 95% CI and p-value, unless otherwise stated.

Table 13 details which endpoints are to be subjected to formal statistical analysis, together with pre-planned sensitivity analyses, making it clear which analysis is regarded as primary for that endpoint. Note, all endpoints compare durvalumab monotherapy and durvalumab and tremelimumab combination therapy versus placebo in all randomized patients (FAS), unless otherwise indicated.

Table 13 Pre-planned statistical and sensitivity analyses to be conducted

Endpoints analyzed	Notes
Progression-free survival	Stratified log-rank tests for:
	
 
Primary analysis using BICR RECIST 1.1 assessments (durvalumab monotherapy versus placebo)
 

	
 
Sensitivity analyses using BICR RECIST 1.1 assessments
 

	1) Interval censored analysis – evaluation time bias
	2) Analysis using alternative censoring rules – attrition bias
	
 
Sensitivity analysis using site Investigator RECIST 1.1 assessments – ascertainment bias
 

	
 
Secondary analysis using BICR RECIST 1.1 assessments (durvalumab + tremelimumab versus placebo and durvalumab + tremelimumab versus durvalumab monotherapy)
 

	Subgroup analysis using Cox proportional hazards models
	Additional analysis using Cox proportional hazards models to determine the effect of covariates on the HR estimate
	Additional analysis using Cox proportional hazards models to determine the consistency of treatment effect between subgroups

Endpoints analyzed	Notes	
Overall survival	Stratified log-rank tests for:	
	
 
Primary analysis (durvalumab monotherapy versus placebo)
 
	
	
 
Secondary analysis (durvalumab + tremelimumab versus placebo and durvalumab + tremelimumab versus durvalumab monotherapy)
 
	
	Sensitivity analysis using a Kaplan-Meier plot of time to censoring where the censoring indicator of the primary analysis is reversed – attrition bias	
	Subgroup analysis using Cox proportional hazards models	
	Additional analysis using Cox proportional hazards models to determine the effect of covariates on the HR estimate	
	Additional analysis using Cox proportional hazards models to determine the consistency of treatment effect between subgroups	
Objective response rate	Cochran-Mantel-Haenszel test for difference in proportions (using Investigator RECIST 1.1 assessments) adjusting for the same factors as the primary endpoint for:	
	
 
Secondary analysis (durvalumab monotherapy and durvalumab + tremelimumab combination therapy versus placebo and durvalumab + tremelimumab versus durvalumab monotherapy)
 
	
PFS at 18 months and 24 months	Kaplan-Meier estimates	
Time to death or distant metastasis	Stratified log-rank test using BICR tumor data (RECIST 1.1)	
Time from randomization to second progression	Stratified log-rank test using site Investigator RECIST 1.1 assessments	
OS at 24 and 36 months	Kaplan-Meier estimates of survival at 24 months and 36 months and analyses following the method described by Klein et al (Klein et al 2007)	
Change from baseline in key symptoms (EORTC QLQ-C30 and QLQ-LC13)	Mixed-model repeated measures analysis	
GHSQoL/Function improvement rate (EORTC QLQ-C30 endpoints)	Presented using summaries and descriptive statistics	
Symptom improvement rate (EORTC QLQ-C30 and QLQ-LC13 endpoints)	Logistic regression	
Time to GHSQoL/Function deterioration (EORTC QLQ-C30 endpoints)	Stratified log-rank test	

Endpoints analyzed	Notes
Time to symptom deterioration (EORTC QLQ-C30 and QLQ-LC13 endpoints)	Stratified log-rank test
Treatment-related symptoms (PRO-CTCAE and PGIS)	Presented using summaries and descriptive statistic

BICR Blinded Independent Central Review; CMH Cochran–Mantel–Haenszel; CTCAE Common Terminology Criteria for Adverse Event; EORTC European Organisation for Research and Treatment of Cancer; GHS/QoL Global health score/Health-related quality of life; ORR Objective response rate; OS Overall survival; PCI Prophylactic cranial irradiation; PFS Progression-free survival; PGIS Patient's Global Impression of Severity; PRO Patient-reported outcome; QLQ-C30 30-Item core quality of life questionnaire; QLQ-LC13 Lung cancer module; SAP Statistical analysis plan.

# 9.5.1.1 Progression-free survival

The primary PFS analysis will be based on the programmatically derived RECIST 1.1 using BICR tumor assessments. The analysis will be performed in the FAS using a stratified log-rank test adjusting for TNM stage (I/II versus III) and receipt of PCI (yes versus no). The effect of durvalumab monotherapy and durvalumab and tremelimumab combination therapy versus placebo treatment will be estimated by the hazard ratio (HR) together with its corresponding confidence interval (CI) (95% and [1-adjusted alpha] × 100%) from a stratified Cox proportional hazards model.

In order to ensure there are at least 5 events within each strata; if there are too few events in the Stage I/II stratification level, TNM stage may be excluded from the models leaving receipt of PCI as the sole stratification factor.

Secondary PFS analyses will be performed using the same methodology as for the primary analysis.

Kaplan-Meier plots of PFS will be presented by treatment group. Summaries of the number and percentage of patients experiencing a PFS event and the type of event (RECIST 1.1 or death) will be provided along with median PFS for each treatment group.

Sensitivity analyses will be performed to assess possible evaluation-time bias that may be introduced if scans are not performed at the protocol-scheduled time points. The midpoint between the time of progression and the previous evaluable RECIST assessment will be analyzed using a log-rank test. For patients whose death was treated as PFS event, the date of death will be used to derive the PFS time used in the analysis. This approach has been shown to be robust even in highly asymmetric assessment schedules (Sun and Chen 2010).

Attrition bias will be assessed by repeating the PFS analysis except that the actual PFS event times, rather than the censored times, of patients who progressed or died in the absence of progression immediately following 2 or more non-evaluable tumor assessments will be included. In addition, patients who take subsequent therapy prior to progression or death will be censored at their last evaluable assessment prior to taking the subsequent therapy. This analysis will be

supported by a Kaplan-Meier plot of the time to censoring where the censoring indicator of the PFS analysis is reversed.

Ascertainment bias will be assessed by analyzing the site Investigator data. The stratified log-rank test will be repeated on PFS using the site Investigator data based on RECIST. Disagreements between Investigator and central reviews of RECIST progression will be presented for each treatment group.

The assumption of proportionality will be assessed firstly by examining plots of complementary log-log (event times) versus log (time) and, if these raise concerns, by fitting a time-dependent covariate to assess the extent to which this represents random variation. If a lack of proportionality is evident, the variation in treatment effect will be described by presenting piecewise HR calculated over distinct time-periods. In such circumstances, the HR can still be meaningfully interpreted as an average HR over time unless there is extensive crossing of the survival curves. If lack of proportionality is found, this may be a result of treatment-by-covariate interactions, which will be investigated. In addition, the Kaplan-Meier curve along with landmark analyses (eg, 1-year PFS rate) will also help in understanding the treatment benefit.

Subgroup analyses will be conducted comparing PFS (per RECIST 1.1 using BICR assessments) between durvalumab monotherapy and durvalumab and tremelimumab combination therapy versus placebo in the following subgroups of the FAS (but not limited to):

- TNM stage (Stage I/II versus III)
- Receipt of PCI (yes versus no)
- Time from end date of cCRT to randomization in this study (<14 days, ≥14 to <28 days, ≥28 days)
- Time from last dose of radiotherapy to randomization in this study (<28 days,  $\ge28$  to <56 days,  $\ge56$  to <84 days,  $\ge84$  days)
- Prior platinum chemotherapy (carboplatin versus cisplatin)
- Prior radiotherapy regimen (daily versus twice daily)
- Best response to CRT (CR versus PR versus SD)
- Sex (male versus female)
- Age (<65 versus  $\ge 65$  years of age)
- PD-L1 status (< 1% versus  $\ge 1\%$ )
- Smoking status (smoker versus non-smoker [never smoker])
- Race/ethnicity

- Geographic region
- WHO/ECOG PS (0 versus 1)

Other baseline variables may also be assessed if there is clinical justification or an imbalance is observed between the treatment groups. The purpose of the subgroup analyses is to assess the consistency of treatment effect across expected prognostic and/or predictive factors. Forest plot(s) will be generated.

No adjustment to the significance level for testing of the subgroup and sensitivity analyses will be made, since all these analyses will be considered supportive of the analysis of PFS.

Cox proportional hazards modeling will be employed to assess the effect of covariates on the HR estimate. A model will be constructed, containing the treatment and the stratification factors, to ensure that any output from the Cox modeling is likely to be consistent with the results of the stratified log-rank test.

Interactions between treatment and stratification factors will also be tested to rule out any qualitative interaction using the approach of Gail and Simon 1985 (Gail and Simon 1985).

Additionally, for each subgroup, the HR (durvalumab monotherapy or durvalumab and tremelimumab combination therapy: placebo) and 95% CI will be calculated from a Cox proportional hazards model with treatment as the only covariate. These will be presented on a Forest plot including the HR and 95% CI from the overall population.

If there are too few events available for a meaningful analysis of a particular subgroup (it is not considered appropriate to present analyses where there are less than 20 events in a subgroup), the relationship between that subgroup and PFS will not be formally analyzed. In this case, only descriptive summaries will be provided.

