## 8.1.1 Central reading of scans

Images, including unscheduled visit scans, will be collected on an ongoing basis and sent to an AstraZeneca-appointed Contract Research Organization (CRO) for QC and storage. Guidelines for image acquisition, de-identification, storage at the investigative site as source data, and transfer to the imaging CRO will be provided in a separate document. Results of these independent reviews will not be communicated to Investigators, and results of Investigator RECIST 1.1 assessments will not be shared with the central reviewers. The management of patients will be based, in part, upon the results of the RECIST 1.1 assessment conducted by the Investigator. Further details of the BICR will be documented in the Independent Review Charter (also referred to as "Imaging Charter").

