# 9.2 Sample size determination

Approximately 965 patients will be recruited globally in order to randomize approximately 724 patients to durvalumab monotherapy (approximately 262 patients), placebo (approximately 262 patients), or durvalumab + tremelimumab combination therapy (approximately 200 patients) over a period of 38 months. Initially, patients will be randomized 1:1:1 to the 3 treatment groups. Following implementation of CSP Version 4, once 600 patients have been randomized, a further 124 patients will subsequently be randomized 1:1 to durvalumab monotherapy or placebo until a total of 724 patients have been randomized.

The primary PFS analysis will occur at the earliest of:

- 1. When approximately 370 PFS BICR events have occurred (70.6% maturity) in the durvalumab monotherapy and placebo treatment groups
- 2. At OS-IA2, if OS-IA2 is statistically significant (durvalumab monotherapy vs placebo)
- 3. 36 months after the last patient randomized

With 370 PFS BICR events, if the true PFS HR is 0.65 for durvalumab monotherapy versus placebo, the study will have approximately 90% power to demonstrate a statistically significant difference in PFS between durvalumab monotherapy and placebo, with an overall 2-sided significance level of 0.5%. The true HR of 0.65 translates to a 5.4 month benefit in median PFS over 10 months on placebo if PFS is exponentially distributed. The smallest treatment difference that would be statistically significant is an HR of 0.743 (Critical value (CV)). A recruitment period of approximately 38 months are expected for the primary PFS analysis. At this time, approximately 309 PFS BICR events are also expected to have occurred in the durvalumab in combination with tremelimumab and placebo treatment groups.

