A sensitivity analysis will be performed to assess possible evaluation-time bias that may be introduced if scans are not performed at the protocol-scheduled time points. The midpoint between the time of progression and the previous evaluable RECIST assessment (using the final date of the assessment) will be analyzed using a stratified log-rank test, as described for the primary analysis of PFS. Note that midpoint values resulting in non-integer values should be rounded down. For patients whose death was treated as a PFS event, the date of death will be used to derive the PFS time used in the analysis. This approach has been shown to be robust to even highly asymmetric assessment schedules (Sun and Chen 2010). To support this analysis, the mean of patient-level average inter-assessment times will be tabulated for each treatment group. This approach will use the BICR RECIST assessments.

Attrition bias

Attrition bias will be assessed by repeating the primary PFS analysis except that the actual PFS event times, rather than the censored times, of patients who progressed or died in the

absence of progression immediately following two, or more, non-evaluable tumor assessments will be included. In addition, patients who take subsequent therapy (note radiotherapy is not considered a subsequent anti-cancer therapy) prior to their last RECIST assessment or progression or death will be censored at their last assessment prior to taking the subsequent therapy. This analysis will be supported by a Kaplan-Meier plot of the time to censoring from the primary analysis where the censoring indicator of the PFS analysis is reversed. This approach will use the BICR RECIST assessments.

• Ascertainment bias

Ascertainment bias will be assessed by analyzing the site investigator data. The stratified log rank test will be repeated on the programmatically derived PFS using the site investigator data based upon RECIST. The HR and CI will be presented.

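### The only attrition-bias analysis of BICR PFS bundles two opposing censoring changes, so it cannot isolate the effect of the missed-visit rule

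*Protocol*

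**What the plan says.** Protocol 9.4.1.2 and SAP 3.2.1 define PFS so that progression or death counts whether or not the patient has stopped treatment or started another anticancer therapy. They make one exception: an event after two or more missed visits (consecutive, in the SAP) is censored at the last assessment before the gap.

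The attrition-bias analysis in protocol 9.5.1.1 changes two things.

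- **Rule 1, restore:** it uses "the actual PFS event times, rather than the censored times, of patients who progressed or died in the absence of progression" after two or more non-evaluable assessments.
- **Rule 2, censor at therapy:** "patients who take subsequent therapy prior to progression or death will be censored at their last evaluable assessment prior to taking the subsequent therapy".

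SAP 4.2.2 keeps both in one analysis; patients who start subsequent therapy "will be censored at their last assessment prior to taking the subsequent therapy". It adds that radiotherapy does not count as subsequent therapy. Protocol Table 13 and SAP Table 7 each list this as a single alternative-censoring analysis. No other planned run applies either rule alone.

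**The concern.** The two rules pull in opposite directions relative to the PFS definition. Rule 1 removes a departure from counting events regardless of later therapy; rule 2 introduces one. A single HR cannot show which rule moved it, or whether two movements cancelled.

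The rules can also act on the same patients. Scheduled scanning ends one scan after RECIST progression (protocol 7.1.1 and 8.1). Management rests at least partly on the investigator's read, and for the central read, "Results of these independent reviews will not be communicated to Investigators". Treatment stops at progression so that another therapy can be used (protocol 4.2.3). A patient with investigator progression that BICR does not confirm can therefore leave scanning, start systemic therapy and die later. Rule 1 restores that death and rule 2 takes it out again.

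At stake is the planned check on missed-visit censoring for a dual-primary endpoint. The forest plot in SAP 4.2.2 would show the bundled result as one row, and a reader could take agreement with the primary HR as evidence that missed visits did no harm.

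**Working it through.** **1. The plan's own PFS figures.** Inputs from protocol 9.2: "if the true PFS HR is 0.65 for durvalumab monotherapy versus placebo, the study will have approximately 90% power", with 370 events, 1:1 allocation and overall two-sided alpha of 0.5%. Schoenfeld: power = Φ(√D/2 × |ln HR| − z). With √370/2 = 9.618 and |ln 0.65| = 0.4308, the product is 4.143.

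- At 0.5%: 4.143 − 2.807 = 1.336, power 90.9% (stated: about 90%).
- At the 0.444% level for the primary analysis: power 90.3%.
- Interim, 308 events at 0.184%: power 74.7% (stated: 75%).
- Critical HRs: 0.744 and 0.701 (stated: 0.743 and 0.700).

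The design figures reproduce. The documents state no figure for the attrition run.

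**2. What the rules do to one patient.** Take a hypothetical patient with investigator progression at week 40, not confirmed by BICR, a follow-up scan at week 48 with no BICR event, and systemic therapy from week 50. The windows are those of SAP Appendix B.

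| Death at | Gap from last scan | Primary | Rule 1 only | Both rules |
|---|---|---|---|---|
| Week 80 | 32 weeks (window 22) | censored, week 48 | event, week 80 | censored, week 48 |
| Week 64 | 16 weeks (window 18) | event, week 64 | event, week 64 | censored, week 48 |

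In the first row the bundled run equals the primary analysis. In the second it removes an event that the primary analysis counts. If therapy began before the week 48 scan, rule 2 would censor at week 40.

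**3. Simulation of the size.** From the documents: medians of 10 and 15.4 months, 38-month accrual, the scan schedule. Assumed, because the documents give no rates:

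- uptake of systemic therapy 20% to 90%
- investigator progression unconfirmed by BICR 0% to 30%
- loss from scanning 1% to 3% per month
- median post-progression survival 14 months in both arms
- 8% of first events being deaths without progression, and 5% clinical progression
- no second BICR chance at the follow-up scan
- cut-off 12 to 36 months after the last randomisation

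Each run used 150,000 patients per arm, an approximate missed-visit window and an unstratified Cox model. Rule 1 was read as reversing the missed-visit rule.

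Share of restored deaths that rule 2 re-censors:

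| Systemic-therapy uptake | Re-censored |
|---|---|
| 20% | 17–19% |
| 30% | 26–28% |
| 50% | 44–46% |
| 60% | 50–57% |
| 80% | 67–75% |
| 90% | 79–84% |

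Scaled to 524 patients, rule 1 restored about 40 to 96 deaths. Rule 2 removed about 2 to 37 events that the primary analysis counts.

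HRs at 80% uptake, cut-off 12 months after the last randomisation, true HR 0.647:

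| Unconfirmed, placebo/durvalumab | Primary | Rule 1 only | Both rules |
|---|---|---|---|
| 15%/15% | 0.661 | 0.672 | 0.662 |
| 25%/10% | 0.743 | 0.734 | 0.754 |
| 10%/25% | 0.585 | 0.614 | 0.580 |

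In the two unequal cases, adding rule 2 moves the HR away from 0.647 and past the primary value. In the equal case it moves the HR closer (distance 0.025 falls to 0.015). With a milder imbalance (18%/12%, cut-off at 24 months, 90% uptake) it moved the HR slightly closer, from 0.704 to 0.699. At high uptake the bundled HR stayed within about 0.02 of the primary HR, while rule 1 alone differed from the primary by up to 0.047.

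**The case against.** The run is openly labelled as alternative censoring, is supportive and carries no alpha, so departing from the primary definition is part of its purpose. That is fair, but it does not explain why two departures share one row.

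Unconfirmed site progression also has its own planned checks in SAP 4.2.2: investigator-assessed PFS, early and late discrepancy rates by arm and, if an important discrepancy appears, imputation of an event at the next visit. Missed-visit and premature-censoring counts and a reversed-censoring Kaplan-Meier plot are planned too. These partly cover the mechanism. None estimates the effect of the missed-visit rule on BICR PFS: the investigator run changes the assessor, the counts give no HR, and the imputation is conditional.

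The HR shifts are modest. On the log scale they are ln(0.754/0.734) = 0.027 and ln(0.580/0.614) = −0.057, against a standard error near 2/√370 = 0.104 for a single log HR. The runs share the same patients, so that standard error overstates the noise in their difference, but the effect is not large.

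Rule 1 alone is no unbiased reference either. It dates the restored event at death, and with 25%/10% discordance and a cut-off at 36 months it gave 0.750 against a primary 0.740, further from the truth.

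**Conclusion.** The point holds in a limited form. The bundled run cannot separate the missed-visit effect from censoring at subsequent therapy, and its agreement with the primary HR is ambiguous. That follows from the text without any assumed rate.

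A reader might go further in three ways that the documents do not support.

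- **That rule 2 re-censors most restored deaths.** No rate is given. In simulation this needed systemic-therapy uptake of roughly 55% to 60% or more, and the range was 17% to 84%.
- **That bundling pushes the HR away from the truth.** The direction depends on assumed discordance, and with equal discordance it went the other way.
- **That the run cannot test attrition at all.** Events in patients with no subsequent therapy, or with radiotherapy only, stay restored. Deaths inside the look-back window already count in the primary analysis.

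This is a cheap improvement to a supportive analysis. It does not affect the primary test or its power.

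**What to change.** In protocol 9.5.1.1 and SAP 4.2.2, and in the tables that list the analyses, specify two runs as separate forest-plot rows:

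1. **Attrition:** the primary rule, with events after two or more missed visits counted at their actual date and no censoring at subsequent therapy.
2. **Subsequent therapy:** the primary rule plus censoring at the last assessment before subsequent systemic therapy.

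Keep the combined run as a supplementary row. Tabulate by arm the events restored by the first rule, those re-censored by the second, and the primary events removed by the second.

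In the same edit, reconcile the trigger wording. The attrition text refers to non-evaluable assessments, while protocol 9.4.1.2 and SAP 3.2.1 say that a non-evaluable result is not a missed visit.

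The cost is SAP and protocol wording, one or two extra model runs and slightly more output. Survival status and subsequent therapy are already collected, so no new data are needed.
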